6.2 Analysis of Secondary Outcomes

To examine the association between differences in pre-treatment and post-treatment EBC concentrations of biomarkers and development of SP, we will conduct 2-group independent t-tests comparing mean change levels (from T0 to T1) in each marker among those who developed SP (expected to be around 10-15 patients) to those who remained free of SP at the study end. We will also conduct various exploratory logistic regression models, if numbers permit, to predict the outcome of SP, using various biomarker values (e.g., T0, difference between T0 and T1, etc.) as key predictors. If numbers permit, we will also examine results from repeated measures logistic regression models, using the three repeated measures of the biomarkers as predictors, and/or using at least one delta score as a predictor. Our goal in such exploratory modeling will be to discern what time points or what differences in EBC biomarkers appear to be most highly predictive of occurrence of SP. We will conduct most of this modeling on a single biomarker at a time; based on biological rationale, bivariate findings, and numbers, we may also explore some modeling where more than one biomarker is included.

We also wish to determine to what degree serum levels of biomarkers correlate with levels of the same biomarkers measured in exhaled breath condensate, and how well these serum markers predict SP. For this latter goal, we will use a similar plan as described in the preceding paragraph.

For the former objective (examining how well serum and breath levels of biomarkers correspond), because we do not hypothesize a priori that these 2 different sources of a biomarker are actually measuring (estimating) the same quantity for any of the markers, we do not expect absolute agreement. We will

A PILOT STUDY OF EXHALED BREATH ANALYSIS TO ASSESS PNEUMONITIS
DEVELOPMENT AFTER CHEMORADIOTHERAPY FOR STAGE III NSCLC
Wake Forest Baptist Comprehensive Cancer Center (WFBCCC)
WFBCCC 98119

thus first examine scatterplots of the serum vs breath measure of each biomarker, and if the association appears monotonic in the scatterplot, we will compute Spearman rank correlations. (If the association appears linear and monotonic, we will compute Pearson correlations.) If an association between a serum and breath measure of a biomarker is non-monotonic, we will attempt to fit a curve describing the association most accurately.

For our final secondary objective (examining the association between microbiome signatures found in pre-treatment EBC and development of SP) we will use cluster analysis methods to determine whether SP and non-SP patients share similar marker profiles. As stated above, this is a pilot study, therefore these cluster analyses will be considered exploratory and hypothesis generating.

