1.0 Introduction and Background

Summary of Pneumonitis in Patient with Stage III NSCLC

Definitive chemoradiotherapy (CRT) followed by consolidative immunotherapy is a standard treatment for locally advanced non-small cell lung cancer (NSCLC) (1, 2). Pneumonitis represents injury to the lungs in the form of acute or chronic inflammation as a result from these treatments. This injury can either be asymptomatic or symptomatic, and may cause cough, shortness of breath, oxygen requirement, or worse. In patients treated with CRT followed by standard of care immunotherapy, symptomatic pneumonitis (SP), defined as Common Toxicity Criteria for Adverse Events (CTCAE) grade 2 or higher pneumonitis, occurs in approximately 15-20% of patients (3, 4). Current treatment of SP is largely dependent on symptom severity. This ranges from observation or anti-tussive medications for mildly symptomatic cases, to prolonged corticosteroid use, oxygen supplementation, or even hospitalization in more severe cases. Rarely, death may result from SP. The most prevalent etiologies of pneumonitis in these patients includes radiation pneumonitis and immune-mediated pneumonitis. Radiation-induced lung injury, which includes radiation pneumonitis and pulmonary fibrosis, occurs with variable severity (from asymptomatic to fatal) in 20% to 50% of patients treated with modern CRT (5, 6). Radiation pneumonitis generally refers to a reversible, subacute inflammatory reaction that occurs within several weeks to months of CRT (7). Immune-mediated pneumonitis, exhibited by focal or diffuse inflammation of the lung parenchyma, occurs in approximately 5% of patients receiving immune checkpoint inhibitors (8).

Currently, it is very difficult to identify patients at high risk of SP prior to treatment and limited data exist to support individualized prophylactic strategies for those at highest-risk of SP (9). Given the relatively sparse tools at hand to predict an individual's risk of developing SP after combined-modality therapy for locally advanced NSCLC, there is a dire need for more sensitive, personalized methods of detecting patients at risk. The main technique presently available to reduce an individual's risk of SP is to limit the radiation dose to normal lung tissue. Prior studies discussed below have demonstrated correlations between serum markers, but these findings have not been routinely employed for risk stratification in current practice.

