Personalized Strategies to Mitigate Pneumonitis Risk Are Lacking

There are guidelines in place for minimizing radiation dose to normal lung tissue with the goal of decreasing the risks of pneumonitis (10). However, the most appropriate dosimetric thresholds are controversial and are rather crude in their ability to predict SP after radiotherapy. Current practice is to apply generic lung constraints to all patients receiving CRT, generally ensuring that the amount of bilateral normal lung tissue receiving at least 20 Gy is less than 30-35%. Such constraints were devised prior to common use of immunotherapy in this patient population. Given that immunotherapy

A PILOT STUDY OF EXHALED BREATH ANALYSIS TO ASSESS PNEUMONITIS
DEVELOPMENT AFTER CHEMORADIOTHERAPY FOR STAGE III NSCLC
Wake Forest Baptist Comprehensive Cancer Center (WFBCCC)
WFBCCC 98119

alone can induce symptomatic pneumonitis, it is unclear if these constraints remain appropriate. Development of biomarker-based risk prediction models of SP may facilitate further investigation of customized prophylactic strategies (i.e. inhaled corticosteroids or short courses of systemic steroids during CRT).

Serum biomarkers including transforming growth factor-beta 1 (TGF- β 1), interleukin (IL)-6, IL-1 α , and IL-10 have been associated with development of SP (11-14). Previous studies have combined both dosimetric and serum TGF- β 1 to estimate the risk of SP (15). However, inconsistent reports and the use of frequent blood draws during CRT has made this approach difficult for patients and clinicians to implement in practice. Additionally, these studies were performed prior to the adoption of consolidative immunotherapy after CRT. Due to these limitations and inconsistencies, better predictive metrics, collected non-invasively, are needed to identify patients at high risk for SP who may benefit from personalized radiation therapy or prophylactic medical therapy.

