2.0 Objectives

This is a prospective pilot study investigating exhaled breath condensate analyses to quantify the variability over time of various biomarkers associated with SP. Compounds of interest have been chosen due to previous studies demonstrating association with pneumonitis in analyses of serum. Our primary hypothesis is that biomarker concentrations will change over the course of treatment (pre-treatment,

A PILOT STUDY OF EXHALED BREATH ANALYSIS TO ASSESS PNEUMONITIS
DEVELOPMENT AFTER CHEMORADIOTHERAPY FOR STAGE III NSCLC
Wake Forest Baptist Comprehensive Cancer Center (WFBCCC)
WFBCCC 98119

2-weeks on treatment, 6-weeks on treatment, and at 1-month post-treatment, Section 2.1.1). Our secondary hypotheses are that these changes in biomarker concentrations will correlate with SP (Section 2.2.1), which we expect to occur in 15-20% of our patient sample, and that these changes will also occur in serum, which will also correlate with SP (Section 2.2.2). Finally, we hypothesize that pre-treatment EBC-derived microbial signatures will be different in patients who develop SP versus those who do not (Section 2.2.3).

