4.2 Data Collection Methods

4.2.1 Clinical Data Collection

Implementation of this prospective observational pilot study has the full support of the Wake Forest Thoracic Multidisciplinary Research Committee. We plan to enroll 50 patients with newly diagnosed locally advanced non-

A PILOT STUDY OF EXHALED BREATH ANALYSIS TO ASSESS PNEUMONITIS
DEVELOPMENT AFTER CHEMORADIOTHERAPY FOR STAGE III NSCLC
Wake Forest Baptist Comprehensive Cancer Center (WFBCCC)
WFBCCC 98119

small cell lung cancer undergoing standard of care chemoradiotherapy. Baseline characteristics including demographics (age, sex, ethnicity, and race), tobacco use history, past medical history (COPD, interstitial lung disease, asthma, etc.), antibiotic and steroid use, and oncologic history (TNM stage, tumor size, location, histology and date of diagnosis) will be recorded. Baseline pulmonary function, tested as a part of routine pre-treatment workup, will be collected if available. Treatment-related factors will be recorded including radiotherapeutic modality (3D conformal radiotherapy, intensity-modulated radiotherapy, or volumetric modulated radiotherapy), detailed volumetric and dosimetric parameters for each patient's individualized radiation plan, as well as type of chemotherapy and immunotherapy used.

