6.0 Analytic Plan

6.1 Analysis of Primary Outcome, Sample Size, and Power

This is a pilot study; therefore, our objectives are exploratory in nature, and we have little to no pre-existing findings reported in the literature to guide our expectations. With this in mind, we plan to recruit a single cohort of 50 patients. In order to be able to examine the questions concerning intra-person variability in biomarker measures over time, and the possible relationships of breath and microbial biomarker signatures with lung cancer outcomes, both pre- and post-radiation treatment measures are needed on each participant. Our goal is to

A PILOT STUDY OF EXHALED BREATH ANALYSIS TO ASSESS PNEUMONITIS
DEVELOPMENT AFTER CHEMORADIOTHERAPY FOR STAGE III NSCLC
Wake Forest Baptist Comprehensive Cancer Center (WFBCCC)
WFBCCC 98119

collect from each patient one pre- (T0) and two post-treatment (T1, immediately post treatment and T2, one month following completion of treatment) samples of breath and serum to be examined. Our target sample size of 50 patients is the target for patients with pre- and post- samples collected. Our main interest is in differences between biomarker levels at T1-T0, where we expect to see the largest differences.

First, for the primary objective of detecting intra-person variability from T1 to T0 in EBC measures, the table below shows different power levels for n=50 patients, using a 2-tailed alpha of 0.05.

Detectable standard deviation units	Power
0.3	0.55
0.4	0.79
0.5	0.93

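### No planned analysis of symptomatic pneumonitis uses the recorded lung dose, so a marker difference between groups could reflect dose rather than information the marker adds

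*Combined protocol and SAP*

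**What the plan says.** Section 6.2 plans "2-group independent t-tests comparing mean change levels (from T0 to T1) in each marker among those who developed SP", set against patients free of SP at study end. It names no covariate and no transformation. Serum markers are to follow a similar plan, so objectives 2.2.1 and 2.2.2.2 share the method. The section adds exploratory logistic and repeated-measures models for SP, to be run only if there are enough patients. T0 and the T0-to-T1 difference are listed there as possible predictors; lung dose is not.

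Elsewhere the protocol gives lung dose a central place. Section 1.0 says the main technique now available for lowering a patient's SP risk "is to limit the radiation dose to normal lung tissue". It also notes that "Previous studies have combined both dosimetric and serum" TGF-β1 to estimate SP risk. Section 4.2.1 records "detailed volumetric and dosimetric parameters for each" patient's radiation plan, and the Section 7.3 calendar includes a radiotherapy detail form. No analysis in Section 6 refers to these data.

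**The concern.** Radiotherapy is given between T0 (before chemoradiotherapy) and T1 (immediately after it), so the change score is directly exposed to dose. If more irradiated lung moves the marker and also raises SP risk, the SP group will show a larger mean change even when the marker says nothing about SP beyond what the radiation plan already shows.

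This bears on the study's purpose. Section 1.0 calls dose thresholds crude predictors and asks for better ones. A marker that only tracks lung dose does not meet that need, and the planned comparison cannot tell it apart from one that does. The risk is that such a marker is carried forward into later prediction work.

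**Working it through.** **Inputs from the documents.** Section 6.1: "Our target sample size of 50 patients is the target for patients with pre- and post- samples collected"; and "the table below shows different power levels for n=50 patients, using a 2-tailed alpha of 0.05". That alpha is stated for the primary within-person analysis; I assume it for the SP test too. Number with SP: Section 6.2 says "expected to be around 10-15 patients", which is 10/50 to 15/50, or 20-30%. Section 2.0 has SP as an outcome "which we expect to occur in 15-20% of our patient sample", which is 0.15 × 50 = 7.5 to 0.20 × 50 = 10 patients. These two statements need reconciling, so I cover both.

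**Inputs assumed.** The documents give no odds ratio of SP per SD of lung dose (range used 1.5-2.5), no dose-marker correlation r (0, 0.3, 0.5) and no T0-T1 correlation ρ (0.3-0.9).

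**Step 1: the plan's own figures.** Paired t-test, n = 50, df = 49, noncentrality d√50. For d = 0.3 / 0.4 / 0.5 the power is 0.548 / 0.792 / 0.934, against 0.55 / 0.79 / 0.93 in Section 6.1. The table reproduces. It covers the primary analysis; no power is given for the SP comparison.

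**Step 2: what the SP t-test can detect.** Noncentrality d/√(1/n₁ + 1/n₂), df = 48. The difference detectable with 80% power is 1.10 SD of change (8 v 42), 1.01 SD (10 v 40) or 0.88 SD (15 v 35).

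**Step 3: effect of leaving dose out.** Simulate standardised dose D; SP from a logistic model in D; change = r·D + √(1 − r²)·noise, with no marker-SP link given D. There are 6,000 runs per cell. Entries are the percentage of runs rejecting at 0.05, t-test / model with dose.

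| SP share | r | OR 1.5 | OR 2.0 | OR 2.5 |
|---|---|---|---|---|
| 20% | 0 | 5.4 / 5.1 | 5.1 / 5.2 | 4.8 / 5.2 |
| 20% | 0.3 | 6.1 / 4.9 | 8.4 / 5.0 | 10.8 / 5.0 |
| 20% | 0.5 | 8.5 / 5.0 | 14.4 / 4.9 | 19.9 / 4.9 |
| 30% | 0 | 4.6 / 4.6 | 5.0 / 5.1 | 4.7 / 4.9 |
| 30% | 0.3 | 6.2 / 4.8 | 8.8 / 4.9 | 11.1 / 4.5 |
| 30% | 0.5 | 9.6 / 5.7 | 16.7 / 5.0 | 24.0 / 4.8 |

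Hand check of one cell (20%, r = 0.5, OR 2.0): the simulated mean difference is 0.327 SD. With 10 v 40 the standard error is √(1/10 + 1/40) = 0.354, so the noncentrality is 0.327/0.354 = 0.92. Against a critical value of 2.01, the rejection rate is about 14%, as tabulated.

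A second setting has 18% SP (inside the Section 2.0 range), log-normal concentrations (log SD 0.75), ρ = 0.4, and dose correlated 0.3-0.5 with the marker level. The t-test on raw change rejects in 6-8% of runs at OR 1.5 and 8-17% at OR 2.0-2.5; with dose in the model the rate is about 5%. The headline of 6-17% comes from this setting. The first setting reaches 24% because it ties dose to the change itself and allows up to 30% SP.

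**Step 4: baseline adjustment, kept separate.** With equal variances and no baseline gap between groups, the ratio of residual variances (T1 adjusted for T0, over change score) is (1 − ρ²)/[2(1 − ρ)] = (1 + ρ)/2: 0.65 at ρ = 0.3 and 0.95 at ρ = 0.9. For a true difference of 0.8 SD of change, 10 v 40, power is 0.60 with the change score and 0.79 / 0.73 / 0.67 / 0.62 with baseline adjustment at ρ = 0.3 / 0.5 / 0.7 / 0.9.

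SP groups are not randomised. If they differ at T0 by g SD and change equally, the adjusted model still targets g(1 − ρ): 0.8 × 0.7 = 0.56 SD at g = 0.8, ρ = 0.3, and 0.5 × 0.3 = 0.15 SD at g = 0.5, ρ = 0.7. In simulation (9 SP patients of 50, g = 0.5-0.8, ρ = 0.3-0.7) it rejects in about 9-30% of runs; the change-score t-test stays at 4-5%.

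**The case against.** The t-test answers the objective as written. Objective 2.2.1 asks whether pre-to-post differences are associated with SP; it makes no claim of value beyond dosimetry. In the Step 3 scenarios, marker change and SP really are associated marginally, through dose. A reader might call the 6-17% a false-positive rate; the documents do not support that for objective 2.2.1. The label fits only the further question of what the marker adds beyond dose. This stands, and it is why the t-test should be kept.

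A reader might also infer that the plan ignores baseline, loses power as a result, and should use T1 adjusted for T0 as the main test. The documents do not support this. A change score uses T0 by construction, and Section 6.2 lists T0 as a possible predictor in its exploratory models. The power gain depends on ρ, which is not given, and falls to about 2 points at ρ = 0.9. As Step 4 shows, adjustment in non-randomised groups changes the quantity estimated.

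The assumed dose effects may be too strong. Section 1.0 calls dose thresholds controversial and crude, and says generic lung constraints are applied to all patients, which narrows the dose range. At OR 1.5 in the 18% setting the excess is small (6-8%). That stands as a limit on size.

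Finally, this is a secondary analysis in a pilot described as exploratory, and dose could be added later. But a dose measure chosen after the results are seen is weaker evidence than one named now. Nor does the small number with SP rule the model out: it restricts logistic models with SP as outcome, whereas here the marker is the outcome and about 50 patients contribute.

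**Conclusion.** The point holds for lung dose. The only unconditional SP comparison is unadjusted, dosimetry is recorded for each patient, and nothing in Section 6 uses it, so the plan cannot separate a marker signal from lung dose.

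On the question of what the marker adds beyond dose, the unadjusted test rejects in about 6-17% of runs with no such contribution, against about 5% with dose modelled. Those figures rest on the assumed odds ratios (1.5-2.5 per SD of dose) and correlations (0.3-0.5). They rise to 24% in the most adverse cell examined and vanish if dose and marker are unrelated.

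It does not follow that the t-test is wrong for objective 2.2.1 or that baseline adjustment should replace it. The gap is worth closing because the data are already being collected, but it does not undermine the primary objective.

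**What to change.** In Section 6.2, keep the change-score t-test as the analysis of objective 2.2.1. Beside it prespecify, for each marker in breath condensate and in serum, a linear model of T0-to-T1 change on SP group and one lung-dose measure chosen before any marker data are examined. The share of lung receiving at least 20 Gy, the quantity constrained in Section 1.0, is one example. State that this model addresses what the marker adds beyond dose, and report both estimates with confidence intervals.

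Optionally, as a sensitivity analysis, report log T1 on SP group, log T0 and the same dose measure. Note that it estimates a different quantity if the groups differ at baseline, and that any power gain depends on the T0-T1 correlation.

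Cost: a paragraph of SAP text, one or two extra models per marker, and one or two degrees of freedom. There is also some loss of precision where dose is related to SP: in simulation, adding dose cost about 1 point of power when dose was unrelated to SP and 2-4 points at an odds ratio of 2.0. No new data are needed.

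### Section 6.2 leaves the estimator for its small-sample logistic models of SP unnamed; Firth's penalised likelihood with an intercept correction would cheaply improve on default maximum likelihood

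*Combined protocol and SAP*

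**What the plan says.** Section 6.1: "we plan to recruit a single cohort of 50 patients", and "Our target sample size of 50 patients is the target for patients with pre- and post- samples collected". Section 6.1 states power only for the primary T1-T0 change, not for any model of SP.

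Section 2.0, on SP: "which we expect to occur in 15-20% of our patient sample". Section 1.0 gives the same background rate: SP "occurs in approximately 15-20% of patients".

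Section 6.2 compares mean T0-T1 change between patients with and without SP by t-test. In that sentence it puts the SP group at roughly 10 to 15 patients. It then says "We will also conduct various exploratory logistic regression models, if numbers permit, to predict the outcome of SP, using various biomarker values". On the same condition it allows repeated measures logistic models with a marker's three measurements as predictors. Most models are to use one biomarker, but "we may also explore some modeling where more than one biomarker is included". Serum markers are to follow a similar plan.

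Section 6.2 does not name the estimator or the interval method. It gives no rule for samples without a finite estimate, and no event count at which the numbers would be judged sufficient.

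**The concern.** Logistic regression with no estimator named will normally be run by maximum likelihood. With few events per coefficient, maximum likelihood gives log odds ratios that on average lie too far from zero, with a long upper tail. This affects even a single marker fixed in advance, so it is separate from any optimism caused by searching over markers and visits.

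Section 6.2 wants these models to show which time points or changes best predict SP. The odds ratios for breath and serum markers are therefore among the pilot's products. If they are inflated and noisier than necessary, markers and visits are harder to compare. A standard alternative lowers both bias and error using the same data.

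**Working it through.** **1. Events available.** Inputs: N = 50 (6.1), SP rate 15-20% (2.0 and 1.0), 10-15 SP patients (6.2).

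- From the rate: 50 × 0.15 = 7.5 and 50 × 0.20 = 10.
- From 6.2: 10/50 = 20% and 15/50 = 30%.

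The 10-15 figure is not reproduced from 15-20%; the ranges meet only at 10. Binomial probabilities of 10 or more events are 0.21 at 15% and 0.56 at 20%. For 15 or more they are 0.005 and 0.06. Both counts are carried forward.

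**2. Events per marker term.**

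- One term: 7.5-10 (or 10-15 by 6.2).
- Three terms: 7.5/3 = 2.5 to 10/3 = 3.3 (or 3.3 to 15/3 = 5).

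**3. Bias in the odds ratio.** The plan gives no figure for these models, so the check is by simulation. The assumptions are not from the documents: n = 50, normally distributed markers, one marker with a true odds ratio of 2 per SD (log 0.693), correlation 0.5 between terms, and 1,200 data sets per row. Relative bias = mean log odds ratio / 0.693 − 1.

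| Events | Terms | ML mean | ML bias | Firth mean | Firth bias |
|---|---|---|---|---|---|
| 8 | 1 | 0.787 | +14% | 0.705 | +2% |
| 8 | 3 | 0.834 | +20% | 0.692 | 0% |
| 10 | 1 | 0.770 | +11% | 0.698 | +1% |
| 10 | 3 | 0.816 | +18% | 0.693 | 0% |
| 15 | 1 | 0.765 | +10% | 0.702 | +1% |
| 15 | 3 | 0.801 | +16% | 0.698 | +1% |

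Monte Carlo error is about 0.02 on each mean, or 0.02/0.693 = 3 percentage points of bias. Further runs with correlation 0.6 between visits, at SP rates of 15-30%, give 9-15% for one term and 15-26% for three. One separate run gave 7% for one term at 30% SP, within simulation error of that range. With a true odds ratio of 1 there is no bias.

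**4. Total error (root mean square error of the log odds ratio, ML then Firth).**

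- One term, SP 15%: 0.58, 0.49.
- Three terms, SP 15%: 0.88, 0.65.
- Three terms, SP 20%: 0.71, 0.57.
- Three terms, SP 30%: 0.59, 0.49.

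Firth is lower throughout, so for the odds ratios less bias is not bought with more variance.

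**5. What Firth costs.** It pulls predicted risks towards 0.5. Mean predicted risk minus observed rate:

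- 8 events, one term: 17.1% − 16.0% = 1.1 points.
- 8 events, three terms: 18.1% − 16.0% = 2.1 points.
- 10 events, one term: 21.0% − 20.0% = 1.0 point.
- 10 events, three terms: 21.8% − 20.0% = 1.8 points.

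In the lowest-risk quarter (8 events, three terms) the true mean risk is 6.6%; Firth gives 9.1% and ML 7.0%. Re-estimating the intercept (FLIC) restores 16.0% and 20.0% exactly and leaves the Firth odds ratios unchanged.

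**6. What Firth does not change.** With three terms and a true odds ratio of 2, the penalised likelihood-ratio test has power of about 24% at 8 events and 28% at 10.

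**The case against.** The strongest reply is that this is a small matter in an exploratory analysis. Section 6.1 calls the objectives exploratory, the t-tests come first in 6.2, and the logistic models are conditional on numbers. Most will have one biomarker. There, at 15% SP, the mean bias is 0.09 against a median standard error of 0.48, about a fifth of a standard error (0.09/0.48 = 0.19). By the median rather than the mean, maximum likelihood gives 0.728 (+5%) and Firth 0.654 (−6%), so neither is exact for a typical sample. All of this stands and limits the weight of the point. It does not remove the gain: Firth has the lower mean bias and the lower root mean square error in every setting tried with a real effect, including 6.2's own upper count of 15 events.

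A reader might infer more than the documents support:

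- **That the plan specifies ordinary maximum likelihood.** It names no estimator; maximum likelihood is only the default reading.
- **That three visits must enter as three coefficients, or that two markers at three visits give six.** The three-term model is one reading of the repeated measures sentence. The six-term model joins two separately conditional options and is not described.
- **That these odds ratios will size a later study.** This is plausible but not stated.
- **That Firth is free of cost.** Uncorrected, it overstates average SP risk, which matters because 6.2 sets out to predict SP.

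**Conclusion.** The point holds as a cheap improvement, not as an error that undermines the study. With about 7.5-15 events, default maximum likelihood would overstate the mean log odds ratio by about 9-15% with one term and 15-26% with three; Firth is within about 3%, with smaller total error. In the one-term models that will make up most of the work, the bias is small beside the sampling error.

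The sizes rest on an assumed odds ratio of 2 per SD, normal markers, correlations of 0.5-0.6 between terms and the default estimator. Skewed cytokine values were not simulated. The conclusion does not depend on which event count is right, but Sections 2.0 and 6.2 disagree on it and need to be reconciled.

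**What to change.** In Section 6.2, state that:

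- all logistic models for SP, for EBC and for serum, are fitted by Firth's penalised likelihood, with profile penalised-likelihood confidence intervals and each marker scaled per SD;
- wherever predicted SP risks or calibration are reported, an intercept correction (FLIC or FLAC) is applied.

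Also reconcile the expected number of SP patients in 6.2 with the rate in 2.0.

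The cost is about two sentences of text and no new data, samples or visits. Reported odds ratios will be somewhat smaller. The change does not address low power or the choice among many candidate models. A stated minimum event count and a cap on terms would be the natural companions for those, but they are a separate decision.

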5.2 Secondary Outcomes

5.2.1 Concentrations of TGF- β 1, IL-6, IL-1 α , and IL-10 (ng/mL) measured in exhaled breath condensate prior to CRT (baseline), at 2 weeks after CRT start, 6-weeks after CRT start (the end of CRT), and 1

A PILOT STUDY OF EXHALED BREATH ANALYSIS TO ASSESS PNEUMONITIS
DEVELOPMENT AFTER CHEMORADIOTHERAPY FOR STAGE III NSCLC
Wake Forest Baptist Comprehensive Cancer Center (WFBCCC)
WFBCCC 98119

month after completion of CRT compared among patients who develop SP versus those who do not. SP will be assessed at each time point and will be defined as presence of CTCAE version 5.0 grade 2 or higher SP (Appendix C).

- 5.2.2 Concentration of TGF- β 1, IL-6, IL-1 α , and IL-10 (ng/mL) measured in serum prior to CRT (baseline), at 2 weeks after CRT start, 6-weeks after CRT start (the end of CRT), and 1 month after completion of CRT:
 - 5.2.2.1 Compared to concentrations of same biomarkers measured in exhaled breath condensate at same time points (see 5.2.1);
 - 5.2.2.2 and compared among patients who develop SP versus those who do not.
- 5.2.3 Microbial signatures measured in exhaled breath condensate prior to CRT, and presence/absence of SP at study end.

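### Section 6.2 makes the serum–breath correlation depend on how the scatterplot looks, so a marker with no visible pattern has no stated route to a coefficient and reported correlations will tend to be too large

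*Combined protocol and SAP*

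**What the plan says.** Objective 2.2.2.1 asks for the association between serum and EBC measures of TGF-β1, IL-6, IL-1α and IL-10. Outcome 5.2.2.1 defines the serum data as "Compared to concentrations of same biomarkers measured in exhaled breath condensate at same time points". Section 6.2 words the aim as finding "to what degree serum levels of biomarkers correlate with levels of the same biomarkers measured in exhaled breath condensate", and adds that, because the two fluids are not assumed to measure the same quantity, "we do not expect absolute agreement".

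The method in Section 6.2 begins with a scatterplot for each marker and then branches:

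- Monotonic appearance: "if the association appears monotonic in the scatterplot, we will compute Spearman rank correlations".
- Linear and monotonic appearance: "If the association appears linear and monotonic, we will compute Pearson correlations".
- Non-monotonic association: "we will attempt to fit a curve describing the association most accurately".

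The section gives no criterion for judging a plot monotonic and does not say what is reported when the plot shows no pattern. It asks for no confidence interval and names no curve family or limit on complexity. No other section calls for a correlation regardless of the plot.

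**The concern.** The question is one of degree, and no correlation is a legitimate answer to it. Each of the three branches presupposes that the analyst has already seen an association. Spearman's rho is defined for any scatterplot, so the visual step is not needed to make the coefficient computable. What the step does is let the data decide whether a number appears.

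With 50 patients, a weakly correlated marker will look monotonic in some samples and shapeless in others. The samples in which it looks monotonic are, on the whole, those in which chance has strengthened the trend. Coefficients reported after that selection are too large on average, and the absent ones are mostly small.

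This matters for a pilot, whose estimates will be used to plan later work. Section 1.0 gives inconsistent earlier findings on serum markers as a reason for including serum. A null or weak correlation with a stated interval would therefore be informative, and it is the result most likely to be lost.

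**Working it through.** **The plan's own figure.** No figure is given for the serum–breath correlation. The only computed figure in Section 6 is the power for the primary T1–T0 change, for 50 patients and "using a 2-tailed alpha of 0.05": 0.55, 0.79 and 0.93 at 0.3, 0.4 and 0.5 standard deviations. A paired t-test with 49 degrees of freedom and noncentrality d√50 gives 0.548, 0.792 and 0.934. The table reproduces and is not affected by this point.

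**Inputs for the check.**

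- n = 50, from Section 6.1: "Our target sample size of 50 patients is the target for patients with pre- and post- samples collected". The number of paired serum and EBC samples at a given visit could be lower.
- Assumed, not in the documents: bivariate normal pairs with true correlation ρ.
- Assumed, not in the documents: the visual judgement behaves like a threshold c on the absolute Spearman coefficient. The written gate concerns shape, and c is a stand-in based on strength, so a range of c is shown. A value of 0.279 is about nominal p < 0.05 at n = 50.

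**Method.** Draw 20,000 samples of 50 pairs for each ρ. Compute r = 1 − 6Σd²/[n(n² − 1)], where d is the difference in ranks. Report r only if |r| ≥ c. Compare with always reporting.

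| True ρ | Always reported | c = 0.10 | c = 0.20 | c = 0.279 | c = 0.40 |
|---|---|---|---|---|---|
| 0: no coefficient | 0% | 51% | 83% | 95% | 99.5% |
| 0: mean absolute r | 0.115 | 0.19 | 0.26 | 0.33 | 0.44 |
| 0.2: no coefficient | 0% | 24% | 53% | 74% | 94% |
| 0.2: mean r | 0.19 | 0.24 | 0.30 | 0.36 | 0.45 |
| 0.3: mean r | 0.28 | 0.31 | 0.34 | 0.39 | 0.47 |
| 0.5: mean r | 0.475 | 0.476 | 0.480 | 0.489 | 0.524 |

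At c = 0.30, about 3% of null markers get a coefficient, so 97% do not. At ρ = 0.2 and the same threshold, 21% are reported and their mean is 0.37.

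**Reading the table.**

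- The always-reported column is essentially unbiased. The Spearman parameter for a normal pair is (6/π)·arcsin(ρ/2), which is 0.19 at ρ = 0.2 and 0.29 at ρ = 0.3, against simulated means of 0.19 and 0.28.
- At ρ = 0 the inflation is in the absolute size of r; the signed mean stays near zero. At positive ρ the signed mean rises too.
- At ρ = 0.2 with c between 0.20 and 0.30, the inflation is 0.30 − 0.19 = 0.11 to 0.37 − 0.19 = 0.18.
- At ρ = 0.5 the inflation is at most 0.014 up to c = 0.279 (0.489 − 0.475), and 0.049 at c = 0.40 (0.524 − 0.475).

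**What unconditional reporting would show.** An approximate 95% interval is tanh[atanh(r) ± 1.96·√((1 + r²/2)/(n − 3))].

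- r = 0: standard error √(1/47) = 0.146, interval −0.28 to 0.28.
- r = 0.2: √(1.02/47) = 0.147, interval −0.09 to 0.46.
- r = 0.3: √(1.045/47) = 0.149, interval 0.02 to 0.54.

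A null result would then be visible, and the reader could see which correlations it rules out.

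**The case against.** The best defence is that plotting first and matching the coefficient to the shape is ordinary good practice. The study is also an exploratory pilot, and the plan is silent about a shapeless plot; it does not forbid a coefficient. An analyst could report the plot and say that it shows no association. The table, moreover, swaps a judgement of shape for a threshold on strength, and that swap produces the selection being measured. A weak correlation that still looks monotonic would be quantified.

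Most of this stands as a limit on size. The magnitudes are conditional on the assumed threshold and cannot be derived from the documents. It does not remove the point. A verbal report of no association does not answer a question of degree, and judging whether a noisy plot of 50 points appears monotonic cannot be separated from how strong the trend is. Looking at the plot is sound; making the coefficient depend on it is the weakness.

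A reader might infer three stronger things that the documents do not support:

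- **That visits will be stacked as independent observations, making intervals too narrow.** Outcome 5.2.2.1 pairs the fluids at the same time points, Section 6.2 does not mention stacking, and no test or interval is stated for this correlation.
- **That a shapeless cloud will be given a best-fitting curve.** The curve branch opens only for an association judged non-monotonic. A cloud with no association does not clearly fall there; the plan leaves it unaddressed.
- **That the plan will overstate how well serum and breath agree.** The target is correlation, and Section 6.2 expressly disclaims absolute agreement.

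**Conclusion.** The point holds as a cheap improvement. Under Section 6.2 as written, whether a marker's serum–breath correlation is quantified depends on the data seen, and a patternless plot has no stated route to a number. The direction is clear as long as a stronger trend is more likely to look monotonic: null and weak correlations tend to drop out, and those reported tend to be too large.

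The size is conditional. With 50 pairs and a visual gate equivalent to an absolute Spearman coefficient of 0.2 to 0.3, about 83–97% of truly null markers would have no coefficient. A true correlation of 0.2 would be reported at about 0.30–0.37 on average, against 0.19 without the gate. A looser gate does less and a stricter one more, and strong correlations are little affected unless the gate is strict. The consequence is confined to one part of a secondary objective.

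**What to change.** Replace the branching rule in Section 6.2 with text such as:

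> For all four biomarkers, Spearman's rho with 95% CI is reported at each time point with paired serum and EBC samples, whatever the scatterplot shows. Scatterplots, Pearson correlations and fitted curves are supplementary description. Visits are not pooled as independent observations.

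The last sentence only carries the time-point pairing in 5.2.2.1 into the analysis section. A correlation of the T1–T0 changes, or a within-patient correlation across visits, could be added but is optional.

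The cost is one paragraph of text, with no new samples or assays. The downside is that some reported coefficients will be smaller.
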